6.3. Secondary Outcomes

For both adult and paediatric populations the outcome measures will be:

- 28-day mortality
- · Ventilator free days
- Length of hospital and critical care stay
- · Thrombotic events
- Requirement for organ support (artificial ventilation, renal replacement therapy, inotropic support)
- Infection organ specific and each episode detailed
- Transfer destination at discharge e.g. home, other medical facility, rehabilitation unit
- Quality of Life at 28 days and 1 year (EQ5D questionnaire and extended Glasgow Outcome Scale for adults, age appropriate PedsQL for paediatric patients)

7. STUDY POPULATION

Estimated number of patients to be enrolled: 5,000

7.1. Setting

The London Air Ambulance (LAA) is the Prehospital Care service for the London Major Trauma System and provides care for injured patients at the scene of the injury. Where possible, adult (only) patients treated by LAA will be recruited under a waiver of consent to allow a

prehospital blood sample to be collected. LAA and other prehospital healthcare providers then triage appropriate Trauma patients to Major Trauma Centres (MTCs). MTCs (UK) provide advanced multi-specialty care for injured patients. The Royal London Hospital (Bart's Health NHS Trust) will be the lead site. The London Air Ambulance will be the only prehospital care provider in the study.

In addition, patients will also be recruited to at major trauma centres as partners within the International Trauma Research Network (INTRN). Such recruitment shall be according to the ACIT protocol herein and shall be conducted under the local governance of individual participating sites.

7.2. Study participants

Only patients who have received prehospital care from the London Air Ambulance and are to be conveyed to a study site *or* patients who arrive at a study site by other means e.g. land ambulance or self-presentation *and* require a trauma team activation will be considered for enrolment into the study. Only those patients undergoing surgical intervention will be considered for the collection of muscle tissue.

As the study is investigating the immediate post-injury phase, patients will be recruited into the study before their full list of injuries is known (before they have X-rays, CT scans, angiograms, operations etc). From our trauma database at the Royal Hospital and existing ACIT study cohort we know that using all major trauma activations, with the exclusion criteria listed below, will provide us with a study population with an injury severity distribution of approximately 35% severe injuries, 55% moderate injuries and 7% minor injuries.

The study will, of necessity, include trauma patients who are unable to give consent for themselves and by definition are in an emergency clinical situation. Patients will be assessed for eligibility to enter the trial according to the criteria set out below. If patients are eligible for entry into the study, following initial screening either in prehospital environment or upon arrival in the Emergency Department, they will be enrolled automatically under a waiver of consent. See Ethics (Section 10) for further details.

The study may also include patients whose first language is not English. There is some evidence that patients from different racial groups have altered responses to injury, and excluding them would bias the study in favour of native English-speaking populations.

Patients will be considered eligible for enrolment in this trial if they fulfil all of the inclusion criteria and none of the exclusion criteria detailed below.

7.3. Inclusion Criteria

Patients eligible for screening are all trauma patients of any age including children:

requiring treatment by the London Air Ambulance medical team (adults only) **and/or**requiring admission to the Emergency Department with a full trauma team
activation (adults and children)

7.4. Exclusion Criteria

Any patient who fulfils any of these criteria will not be considered for inclusion in the study:

- Transfers from other hospitals
- Burns >5% total body surface area
- >120 mins have lapsed since time of injury
- Deemed inappropriate for recruitment by an independent clinician (e.g. mass casualty event or futility)

8. STUDY DESIGN

ACIT II is a prospective cohort multicentre observational study. It will follow the clinical course of trauma patients from injury in the prehospital phase of care and/or at admission to the emergency department and for the first 28 days. Blood samples and, in some patients, muscle biopsies will be analysed for markers of activation of the coagulation and inflammatory systems. These biomarkers will be correlated with patient injury patterns, trauma-induced physiological disturbances and subsequent clinical course and outcome.

8.1.ACIT SWIFT

ACIT-SWIFT is a sub-study of the primary ACIT study to enable a wider patient recruitment nationwide, and pool resources that are being utilized to deliver the a national trial called SWiFT which will recruit bleeding trauma patients in the prehospital phase of care. Patients enrolled into SWiFT are a specific patient subgroup (major trauma haemorrhage) of interest for the primary ACIT study and hence samples and data will be directly relevant for the general aims and hypotheses. ACIT SWIFT will specifically help to understand the treatment effect of whole blood transfusion after injury through a single blood sample taken on admission (post-dosing of the SWIFT intervention) in combination with data collected as part of the SWIFT trial – for ACIT SWIFT sub study details and paperwork please refer to appendix 4

9.0 STUDY PROCEDURES

9.1. Informed Consent

All participants will be recruited under an emergency waiver of consent. Written informed consent or agreement to continue in the study must be obtained from the participant, personal consultee or professional consultee (independent clinician), after explanation of the aims, methods, benefits and potential hazards of the trial.

This research study focuses on the very early post-injury phase (time of injury and first few hours), and is investigating the long-term effects of injury and physiological derangements seen at this time. Most, but potentially not all, participants will be incapacitated at the time of eligibility (critical injury, mechanical ventilation, sedation), such that the Mental Capacity Act (England; 2005) provides guidance. Patients will be recruited within 2 hours of their injury, and those who are not unconscious have recently been through a major psychologically disturbing event, may have been a victim of violence, and are often in pain. As such they may be unable to comprehend, or it may be inappropriate to discuss, the details of a complex research trial at this time. This is also a particularly stressful time for relatives and families, an important consideration when the intervention under investigation is time sensitive. All participants will be enrolled in the study with a waiver of consent without informed participant consent due to the emergency nature of the study thus a waiver of consent will be applied for automatic study enrolment. This study requires that eligible patients are

enrolled as close to the time of injury as possible. As injury is an unexpected event, it is uncommon that relatives are present at the time of hospital admission.

Following hospital admission several approaches to obtaining consent will be used, depending on the mental capacity of the patient and availability of Personal Consultees (relative or friend). In the first instance, if a personal consultee is unavailable and the patient lacks mental capacity, a professional consultee (typically the trauma team leader who is a doctor independent of the research study) will be approached within 24 hours to provide consent for the patient to continue in the study. See Section 11 (Ethics) for a full explanation of the consenting process.

Our standard operating procedure for obtaining consent is included in appendix 2.

9.2. Screening and recruitment

All adult trauma patients (aged 16 and over) who are treated by London Air Ambulance, or trauma patients of any age who are admitted to the emergency department via a trauma team activation will be screened for eligibility to ACIT II. As most trauma patients will be incapacitated at the time of screening it is anticipated that a waiver of consent will be used followed by initiation of the informed consent process at a time appropriate from the participant as described in Section 9.1.

9.3 Schedule of study interventions

Study Activity	Prehospital	Emergency Department	HR 24	HR 48	HR 72	Day 3-7	Day 7	Day 8-288 - 28 days	Discharge/	1-year follow up
Demographics	Adults only	Х								
Injury characteristics	Adults only	Х								
Physiological observations	Adults only	Х	Х	Х	Х	Х	Х	Х		
Organ score (SOFA)			Х	Х	Х	X	X	X	X	
Infections			Х	Х	Х	Х	Х	Х		
Thrombotic Events			Х	Х	Х	Х	Х	х		
Adverse events			Х	Х	х	Х	Х	х		
Blood Sampling*	Adults only	Х	Х		Х		Х			
Muscle biopsy			(X)	(X)	(X)	(X)				
Quality of Life assessment									Х	Х
GOS-E									Х	Х

^{*}All patients with have one blood sample taken on admission at the same as routine clinical blood tests. Bleeding patients requiring blood transfusion will have further samples taken after transfusion of the 4th, 8th and 12th unit of red blood cells in conjunction with routine clinical blood tests. (X) Muscle biopsies will only be taken during a planned or emergency surgical procedure as part of routine clinical care

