NHS REC National Health Service Research Ethics Committee

NHS R&D National Health Service Research & Development

Participant An individual who takes part in a clinical trial

PI Principal Investigator

PIS Participant Information Sheet

QA Quality Assurance
QC Quality Control

RCT Randomised Controlled Trial

REC Research Ethics Committee

SAE Serious Adverse Event

SDV Source Document Verification
SOP Standard Operating Procedure

Sequential Organ Failure Assessment

SSA Site Specific Assessment

SOFA

TMG Trial Management Group

TSC Trial Steering Committee

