Research to date has predominantly focused on adult trauma patients, yet there is an expanding geriatric population who are increasingly sustaining multisystem injuries on the background of poor physiological reserve. This requires a greater understanding of the physiological responses in senescence.

Prehospital sampling

Findings from samples collected within minutes of injury, and our own preliminary data from ACIT II suggest a number of coagulation and inflammatory pathways are activated and/or deranged in the hyperacute period after trauma e.g. <60 minutes. Expanding our research capability to the patient as close to the point of injury will help characterise and understand early physiological and biochemical changes. Understanding whether these very early changes determine clinical outcome, and whether there are novel ways to modulate the response to injury are key research priorities.

Inclusion of paediatric patients

The paediatric population are grossly under-represented in human discovery trauma science with the vast majority of studies specifically excluding children. Trauma however remains a significant disease burden in this population group. Injury profiles, physiological response and management strategies for children are different compared to adults. In part this is due to their physical and physiological characteristics e.g. body size, head size, fat proportion, and reduced bone strength but increased bone pliability. These factors influence how energy from an accident is distributed and consequently children can have severe internal organ injury without bony fractures. Children are much more susceptible to hypothermia, which is known to worsen coagulopathy and organ dysfunction. In addition, clinical examination and vital signs can often be misleading as children are able to physiologically compensate for blood loss to a greater extent than adults. Classically paediatric patients may display a relatively normal physiology up to a point, before sudden and catastrophic circulatory collapse.

The vast majority of clinical evidence which guides trauma practice is translated from adult patients without dedicated paediatric evaluation. Characterisation of key pathways in coagulopathy, organ injury and MODS and therefore evidence to guide management of trauma and haemorrhagic shock in children is wholly inadequate. An important evidence gap exists in our understanding of the paediatric response to injury and blood transfusion, drivers

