To process and store samples for subsequent proteomic, transcriptomic, lipidomic and genomic techniques to identify new loci for investigation, targeting drug discovery and identification of genetic susceptibility to poor outcome following trauma.

Hypothesis ACIT:4A

There are signature transcriptomic, proteomic and lipidomic profiles associated with the risk of post-traumatic MODS and other adverse outcomes. Specific changes in circulating leukocytes and parenchymal cells occur in organs remote from the injured site and are associated with MODS.

Hypothesis ACIT: 4B

Children develop a specific transcriptomic and proteomic response to tissue trauma and hypoperfusion that is protective against post-traumatic organ injury and MODS.

AIM 5: Trauma DNA Bank

To process and store samples for subsequent DNA typing and analysis. There appears to be a background race and genetic susceptibility to the effects of trauma. These alterations may well lie within the coagulation and inflammatory systems. Early identification of patients at risk may, in the future, allow therapy to be targeted depending on patients' racial background or even specific genetic make-up.

Hypothesis ACIT:5A

There are genetic mutations of coagulation and inflammatory genes (e.g. Factor V Leiden, Prothrombin 20210, Mannose Binding Lectin) that may protect against or increase susceptibility to the effects of tissue trauma and hypoperfusion.

Hypothesis ACIT:5B

There are Haplotype-specific (and thus race-related) variations in susceptibility and response to tissue trauma and hypoperfusion.

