6.2. Primary Outcomes

For both adult and paediatric populations the outcome measures will be:

Blood products transfused in the first 24 hours

Incidence & severity of acute organ injury & MODS

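### SOFA is the only organ score named for a primary outcome that covers children of any age, and no age-adapted version or paediatric MODS definition is given

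*Protocol*

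**What the plan says.** Section 6.2 of the Protocol introduces the primary outcomes with "For both adult and paediatric populations the outcome measures will be" and lists, as one of two, "Incidence & severity of acute organ injury & MODS". Section 7.3 sets no lower age limit: "Patients eligible for screening are all trauma patients of any age including children". The blood-volume bands in section 9.4.2 start at 0 to 2 years, so infants and toddlers are expected.

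The schedule in section 9.3 has one row for organ function, "Organ score (SOFA"), ticked at 24, 48 and 72 hours and on to discharge. The abbreviations list expands the term as "Sequential Organ Failure Assessment", and no paediatric variant is listed in the part shown. Section 9.4.4 adds that organ dysfunction is scored daily, without naming an instrument or an age rule.

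On children, section 5.2 states: "Injury profiles, physiological response and management strategies for children are different compared to adults". It also warns that their vital signs can mislead. Section 6.3 uses a separate quality-of-life tool for them ("age appropriate PedsQL for paediatric patients").

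**The concern.** SOFA turns measurements such as blood pressure and creatinine into points. If the cut-offs are fixed at adult values, a child's points depend partly on what is normal at that age and not only on organ dysfunction. Normal values change through childhood, so the error would change with age too, and would probably be largest in the youngest.

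The main risk is inside the paediatric cohort. Hypothesis 2D relates children's immune responses to organ injury and MODS. Hypothesis 4B reads "Children develop a specific transcriptomic and proteomic response to tissue trauma and hypoperfusion that is protective against post-traumatic organ injury and MODS". Aim 3 plans a prediction model for organ injury that covers paediatric patients. If both the biomarkers and the scoring error vary with age, a biomarker can appear linked to MODS, or protective against it, because both follow age. Any pooled analysis, or any table of MODS by age group, carries the same risk.

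**Working it through.** **1. Is there an age rule anywhere in the Protocol?** The Protocol gives no figure to reproduce on this point: section 10 has no power calculation for the main study, and there is no MODS rate and no SOFA threshold. The check is therefore of the text. Four items can be set side by side:

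- *Quality of life*: one undivided row in the schedule. Section 9.4.5 supplies the rule (EQ-5D in adults, PedsQL in children).
- *GOS-E*: no age label in the schedule. Section 9.4.5 limits it to adults.
- *Muscle biopsy*: no age label in the schedule. Section 9.4.3 limits it to adults.
- *Organ score*: no age label in the schedule, and no section supplies a rule.

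A missing label in the table proves little, since three other rows also lack one. For those three the text fills the gap. For SOFA it does not. A site that follows the Protocol as written would score a toddler with SOFA as named.

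**2. What fixed adult cut-offs would do to single components.** The inputs here are assumptions and not Protocol figures: one cardiovascular point for mean arterial pressure below 70 mmHg, and the first renal point at creatinine 110 µmol/L.

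- Cardiovascular: with an assumed normal toddler pressure of 55 to 65 mmHg, the whole range lies below 70. A well toddler scores 1 point each time.
- Renal: the rise needed to score is 110/b, where b is the child's baseline. At an assumed b = 30, 110/30 = 3.7-fold. If b were half that (15), 110/15 = 7.3-fold. If it were double (60), 110/60 = 1.8-fold.

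The first error adds points and the second withholds them. They need not cancel, and a single shift of the total would not repair both.

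**3. What misclassification could do to an observed MODS rate.** This is an illustration, and every input is assumed. Observed rate = sensitivity × true rate + (1 − specificity) × (1 − true rate). Take a true rate of 20% in both age groups.

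- Adults, sensitivity 0.90, specificity 0.95: 0.90 × 0.20 + 0.05 × 0.80 = 0.18 + 0.04 = 22%.
- Children, sensitivity 0.70, specificity 0.95: 0.14 + 0.04 = 18%.
- Children, sensitivity 0.90, specificity 0.80: 0.18 + 0.16 = 34%.

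The spurious child-minus-adult difference runs from 18 − 22 = −4 to 34 − 22 = +12 percentage points, and is zero if accuracy is equal. The sign is open.

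**4. Which analyses use paediatric MODS?** In 1D the quantity contrasted with adults is the coagulopathy. In 2D it is the immunological signature, and MODS is the outcome to which responses are related. In 4B MODS is the outcome of an association in children. In Aim 3 organ injury is the modelled outcome. None of these is a contrast of MODS rates between children and adults.

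**The case against.** The best case for the Protocol has four parts.

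- *The schedule does not show that the adult score is used in children.* The adults-only labels sit in cells of the prehospital column, because children have no prehospital sampling. They do not mark whole rows, and SOFA has no prehospital entry to label. This stands: nothing follows from the absence of that label.
- *The harm depends on thresholds that the Protocol does not print.* This also stands as regards size. It does not remove the gap in the text, which needs no threshold to see: one score, all ages, no age rule.
- *MODS is never defined from SOFA.* Correct. One extra cardiovascular point is not a MODS diagnosis, and the route from points to MODS status is not given. This limits what can be claimed. It is also a reason to state the definition.
- *Cut-offs and scoring rules can sit in an analysis plan or scoring manual.* Partly so, and one may exist. But the score is an instrument applied daily during follow-up, and section 9.4.4 says that outside critical care it is not routine data. A later analysis plan can re-derive it only from raw components. The schedule lists physiological observations at similar times, but the Protocol does not say that every component of the score is recorded.

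A reader might also infer that comparisons of children with adults will be biased. The Protocol does not support that, because no stated hypothesis compares MODS rates between the two groups.

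**Conclusion.** The point holds in a limited form. A primary outcome declared for children of any age is tied to one named organ score, with no age-adapted version, in a Protocol that stresses how children's physiology differs and adapts other measurements to age. If SOFA is applied unmodified, organ dysfunction in young children may be misclassified to a degree that depends on age. The analyses exposed are the biomarker-MODS associations in children (2D, 4B), the paediatric organ-injury model under Aim 3, and any pooled or descriptive MODS comparison by age.

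It would be tempting to say that paediatric MODS will be misclassified. That would require knowing that the unmodified score is used, that its cut-offs are unsuitable for children, and how points become MODS. The Protocol states none of these. The component figures and the −4 to +12 point range rest wholly on the assumptions listed, and neither the size nor the net direction of the error is established.

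**What to change.** In sections 6.2 and 9.3, state that patients under 16 (below the adult limit in section 9.2) are scored with a named, age-adapted paediatric SOFA and adults with SOFA. State the MODS definition for each age group. Require the raw components of the score on the CRF, so that either version can be derived and checked. Rescore children already enrolled wherever the raw components are held, and report how many could not be rescored.

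The cost is a change to the scoring table and some rescoring. An age-adapted version that uses the same underlying variables needs no new measurements. The main limit is past data: where only a total score was kept, that child's value cannot be corrected.

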9.4. Study Intervention

9.4.1 Blood samples

Trauma patients will have blood samples drawn to measure activation of coagulation, fibrinolysis, endothelial injury and the immune system. The maximum sample volume at each time point will be 40mls (maximum 30mls during bleeding time point samples). Samples will be collected in the Emergency Department at admission (Hour 0) and then 24±2 hours, 72±12 hours and at 7 days (±24 hours) post admission. Patients who are actively bleeding will have additional samples (30ml) taken after administration of the 4th, 8th and 12th units of red blood cells, if used.

Adult patients (>16 years old) treated by the London Air Ambulance medical team will have one additional sample taken in the prehospital phase upon their arrival and as close to the time of injury as possible. Prehospital samples will be prefixed PH to indicate a sample obtained prior to Hour 0 baseline (hospital admission) to ensure consistency with previous patients recruited to the ACIT II study.

Severe trauma patients not enrolled in the study would normally have blood samples drawn at minimum at 0, 12 and 24 hours and daily thereafter. Most trauma patients have blood tests drawn more frequently, especially those who have signs of hypoperfusion, coagulopathy, ongoing blood loss or those that are mechanically ventilated. As most major trauma patients have an arterial or central line placed, particularly during the first 24hours when the majority of samples will be taken, most blood draws will not be painful to the patient. When this is not the case, we will we will coordinate our blood draws with those of clinical need whenever possible, to minimise number of needle-sticks. We will not be able to use blood that has already been collected and placed into specimen tubes as our samples will require specific handling and processing.

Rationale for sequential blood sampling

(1) The activation pattern of coagulation following trauma is a dynamic process and the full picture will not be apparent on a single blood draw immediately following injury. Some coagulation factors are used up and the levels of others increased with increased genetic expression. Characterizing these patterns of altered coagulation

would have major implications for the treatment of coagulopathy. How this change occurs is currently unknown, but would be identified by this protocol.

- (2) A prolonged shock state has a known poor outcome. This may be due to continued activation of the coagulation and inflammation systems. Further a procoagulant and depressed immunological state has been identified late in severely injured trauma patients and may extend for many days after injury. Serial measurements up to Day 7 will allow us to detect these changes and correlate them with injury and physiological factors.
- (3) Medical therapy in terms of fluid and blood transfusions may affect these processes but to what degree and in which direction is currently unclear. Trauma patients receiving more than two blood transfusions are known to have a worse outcome. Serial sampling allows us to assess the impact of fluid and blood resuscitation on the coagulation and immune systems.

